3.2 Recruitment, screening and informed consent procedure

Patients will be mainly recruited from our established THC cohort of COPD patients ¹¹ by dedicated study nurses of the Lungenzentrum St. Gallen at the Kantonsspital St. Gallen (phone calls and, if necessary, other channels of communication). New participating patients will also be acquired, namely through ongoing recruitment by the referring physicians in daily practice. All referred COPD patients will be screened systematically by our study nurses on a daily basis. Screening procedures for study inclusion involve routine daily practices. Eligible patients will be informed about the study through personal communication and, if willing to participate, provided with the dedicated informed consent sheet sent along with this proposal. Written informed consent is a prerequisite for study inclusion. No compensation payments will be distributed.

3.3 Study procedures

All patients will be followed using the THC procedure as previously described ^{11,12}. Specifically, the CAT score is measured once per week and patients answer questions on a daily basis that aim at the early detection of AECOPD. The study duration is one year per patient.

In addition, we will measure body composition (e.g., FFMI and fat share) by direct segmental multi-frequency bioelectrical impedance analysis (BIA) and/or dual-energy X-ray absorptiometry (DXA), HGS (with a dynamometer) and biochemical parameters (e.g., CRP, protein, albumin, 25-OH vitamin D3). These measurements will take place at baseline and after 6 and 12 months. Furthermore, patients are provided with a pedometer to record step count and/or an accelerometer to record overall movement/distance traveled. This might be complemented by a standardized sit-to-stand physical test at each visit (baseline, 6 and 12 months). We will assess the nutritional status by standardized questionnaires (Nutritional Risk Screening [NRS] 2002; in case of malnutrition, "Nutritional Assessment" according to local guidelines) and provide nutritional support/therapy by professional personnel. In the final analysis, receipt of nutritional support/therapy will be one parameter stratified for. Nutritional parameters will be assessed at baseline and after 6 and 12 months. Schedule of assessment in appendix 1.

3.4 Withdrawal and discontinuation

Patients are withdrawn from the study by virtue of their own will at any time.

4 STATISTICS AND METHODOLOGY

4.1. Statistical analysis plan

A sample size of 85 patients is envisaged to be able to detect a significant association (expected correlation coefficient $r=0.30$) between Δ FFMI (1 year vs. baseline) and the patients' exacerbation rate with 80% power at a 5% significance level (two-sided).

The evolution of the FFMI will be analyzed using linear regression. The association between the FFMI and the occurrence of AECOPD will be evaluated using the Andersen-Gill formulation of the Cox proportional hazard model as well as joint modeling useful for the analysis of recurrent time-to-event data (exacerbation) with time-varying predictors (FFMI). The association between

FFMI and CAT will be estimated using linear mixed models or alternately generalized estimating equations.

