1 BACKGROUND AND PROJECT RATIONALE

A low body mass index (BMI) has been described as an independent risk factor for mortality in subjects with chronic obstructive pulmonary disease (COPD), while the association was strongest in patients with severe COPD ¹. Additionally, weight loss in the course of the disease was associated with increased mortality ².

A low fat free mass index (FFMI) was also associated with increased overall and COPD-related mortality, even in subjects with normal BMI ³. FFMI seems to be a better predictor of disease severity regarding the degree of chronic dyspnea, forced expiratory volume in 1 second (FEV1), FEV1/forced vital capacity (FVC) ratio and stage of disease than BMI ⁴. Patients with the constellation of abdominal obesity, normal weight and low muscle mass have an increased cardiometabolic risk ⁵. FFMI also correlates with quality of life ⁶. Sarcopenic obesity (SO) is associated with worse physical performance and higher systemic inflammatory burden compared with other body composition phenotypes in COPD ⁷. Sarcopenia affects 15% of patients with stable COPD and impairs function and health status. Sarcopenia does not impact on response to pulmonary rehabilitation (PR), which can lead to a reversal of the syndrome in select patients ⁸. Body composition evaluation is useful for the assessment of COPD patients referred to pulmonary rehabilitation and should be routinely performed ⁹. A well-balanced diet is beneficial to all COPD patients, not only for its potential pulmonary benefits, but also for its proven benefits in metabolic and cardiovascular risk ¹⁰.

If our hypothesis proves to be true, the clinical consequence would be the need to systematically include nutritional assessment / therapy and other measures to reduce malnutrition and sarcopenia in the clinical routine of treating COPD patients to reduce overall risk of acute exacerbation of COPD (AECOPD) and improve quality of life.

The study is of risk category A since there are no relevant risks for participating patients (the study poses no additional risks to the patients compared to routine care).

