2 PROJECT OBJECTIVES AND DESIGN

2.1 Hypothesis and primary objective

The primary objective is to investigate the association between physical activity, malnutrition and sarcopenia and the occurrence of AECOPD / the evolution of the COPD assessment test (CAT) over 1 year in a cohort of COPD patients. We hypothesize that being malnourished and/or sarcopenic at baseline and a decline of FFMI over time is associated with an increased rate of AECOPD and an increased (or increasing) CAT score.

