2.2 Primary and secondary endpoints

The primary endpoint is the rate of exacerbation depending on the explanatory variables FFMI, hand grip strength (HGS) and C-reactive protein (CRP), measured at baseline, after 6 and after 12 months. We will examine the correlation between the evolution of FFMI/HGS/CRP and the occurrence of AECOPD / the evolution of the CAT.

Secondary endpoints include further parameters from our COPD cohort, such as physical activity and further biochemical markers (e.g., protein, albumin, 25-OH vitamin D3), which will be analyzed by descriptive statistics (including cross-sectional and longitudinal analyses).

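### The AECOPD models in 4.1 carry only a time-varying FFMI, so one coefficient mixes level with change and no baseline malnutrition or sarcopenia status is tested

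*Combined protocol and SAP*

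**What the plan says.** Section 2.1 links two exposures to exacerbations: "being malnourished and/or sarcopenic at baseline and a decline of FFMI over time is associated with an increased rate of AECOPD". Section 2.2 states "The primary endpoint is the rate of exacerbation depending on the explanatory variables FFMI, hand grip strength (HGS) and C-reactive protein (CRP"), measured at 0, 6 and 12 months, and adds "We will examine the correlation between the evolution of FFMI/HGS/CRP and the occurrence of AECOPD".

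Section 4.1 sets the sample size for an association "between Δ FFMI (1 year vs. baseline) and the patients' exacerbation rate with 80% power", with r = 0.30, 85 patients and a two-sided 5% level. For the exacerbation analysis it then says "The association between the FFMI and the occurrence of AECOPD will be evaluated using the Andersen-Gill formulation of the Cox proportional hazard model", followed by a joint model described as useful for "recurrent time-to-event data (exacerbation) with time-varying predictors (FFMI"). It also plans a linear regression for the course of FFMI itself, which is not linked to exacerbations.

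On the baseline side, section 3.3 says "We will assess the nutritional status by standardized questionnaires (Nutritional Risk Screening [NRS] 2002") and also schedules body composition and HGS at 0, 6 and 12 months. The final analysis is to be stratified for receipt of nutritional support. Section 1 cites "Sarcopenia affects 15% of patients with stable COPD". The protocol gives no definition of sarcopenia, and 4.1 names neither NRS 2002 nor HGS.

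**The concern.** The hypothesis makes two statements, and the exacerbation models offer one predictor. If FFMI enters as its current value, a patient who has always had a low FFMI and a patient who has just lost muscle contribute to the same coefficient. A significant result may then reflect level alone, and a null result says little about decline.

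The baseline half is worse served: malnutrition or sarcopenia status has no model term, no definition and no statement of what effect could be detected. Section 1 says that a confirmed hypothesis would mean building nutritional assessment and therapy into routine COPD care. A reader would need to know which half had been supported before drawing that conclusion.

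**Working it through.** **Inputs from the protocol.** N = 85, r = 0.30, 80% power, two-sided 5% (4.1); visits at 0, 6 and 12 months and one year of follow-up (3.3); sarcopenia in 15% (section 1).

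**Assumed, not in the protocol.** 1.2 exacerbations per year, gamma frailty variance 0.8, baseline FFMI SD 2.2 and 1-year change SD 0.75 kg/m², baseline and change independent.

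**Step 1: the plan's own figure.** Fisher z: n = ((1.960 + 0.842) / atanh(0.30))² + 3 = (2.802 / 0.3095)² + 3 = 84.93, rounded up to 85. It reproduces.

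**Step 2: what is powered and what is modelled.**

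| Part of the hypothesis | Power statement | Term in the AECOPD models of 4.1 |
|---|---|---|
| FFMI decline | 80%, as a ΔFFMI correlation | None stated; only FFMI, time-varying |
| Baseline malnutrition or sarcopenia | None | None stated |

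**Step 3: why one coefficient mixes the two.** Write FFMI(t) = B + D(t), with B the baseline value and D(t) the change since baseline. A term β·FFMI(t) equals β·B + β·D(t), so level and change are forced to share one β. Suppose risk follows change only, with r = 0.30, and let k = SD(B) / SD(Δ). Even the 12-month value, which contains the whole change, then correlates with the exacerbation rate at only 0.30 / √(1 + k²). Power is about Φ(√82 · atanh(r) − 1.96):

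| k | r | Power at N = 85 |
|---|---|---|
| 0.5 | 0.268 | 70% |
| 1 | 0.212 | 50% |
| 2 | 0.134 | 23% |
| 3 | 0.095 | 14% |

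This is a favourable case. If each FFMI value is carried forward to the next visit, the 12-month value enters no at-risk interval in a one-year follow-up, and that form of the Andersen-Gill model never uses the powered 1-year change.

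**Step 4: simulation at N = 85.** Andersen-Gill was approximated by a piecewise Poisson model with patient-clustered variance. The decline effect was set to give r = −0.30 between ΔFFMI and the exacerbation count. A log rate of −0.3 or −0.4 per SD of level is a rate ratio of 0.74 or 0.67. Share of trials significant:

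| What truly matters | Single FFMI(t) term | ΔFFMI correlation |
|---|---|---|
| Neither | about 7% | about 5% |
| Decline only | about 7-10% | 79-84% |
| Level only, rate ratio 0.74 per SD | 58-59% | about 5% |
| Level only, rate ratio 0.67 per SD | about 80% | about 5% |
| Both (level −0.3 to −0.42 per SD) | about 59-83% | not needed here |

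With other SD ratios and effect sizes, the decline-only figure for FFMI(t) ranged from about 5% to 42%. The joint model itself was not fitted. A current-value term on an error-free linear trajectory, used as a stand-in, gave 10-11% for decline only.

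**Step 5: baseline status.** 85 × 0.15 = 12.75, about 13 patients. With a small-sample-corrected variance, power at 15% prevalence is 20% for a rate ratio of 1.5, 43-47% for 2.0, 68% for 2.5 and 80% for 3.0. At 25% prevalence it is 57% for 2.0 and 81% for 2.5.

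**Step 6: separate terms.** Change from baseline to the most recent visit is zero for everyone until month 6, so only events in months 6-12 inform it. Its power is about 66-69% under the same assumptions with all patients measured. It depends on how steady the decline is. For 0-6 month change against events in months 6-12, runs gave 69% with linear change, 42% with independent half-years and 38-48% with a measurement SD of 0.3.

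**The case against.** The strongest reply is that the plan never gives 80% power to an Andersen-Gill coefficient. Section 4.1 ties it to ΔFFMI against exacerbation rate, and 2.2 announces that correlation, so decline does have an analysis. This stands. A reader might infer that the sample size is wrong or that decline goes unanalysed; the documents support neither.

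A second reply is that silence on the form of the FFMI term is not a commitment to one coefficient, and that a joint model can carry a slope. Also true, but 4.1 does not say that it will. The choice between level and slope is left open until the data have been seen.

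A third is that 2.1 expects both effects to act, and the single term then keeps about 59-83% power. This stands against any claim that power collapses. It does not help interpretation, because the coefficient still cannot say which effect produced it.

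A fourth is that baseline FFMI and HGS are among the explanatory variables in 2.2, so the baseline half is not wholly without variables. Correct. The gap is narrower: no status, definition or cut-off for malnutrition or sarcopenia, and no such term in 4.1. The count of about 13 covers sarcopenia alone, whereas 2.1 counts malnourished and/or sarcopenic patients, who may be more numerous.

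Finally, 2.3 calls the study exploratory. That lowers the weight of the point but does not remove it.

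**Conclusion.** The concern holds as a mismatch between hypothesis and model. Followed as written, the AECOPD models do not separate FFMI level from FFMI change and do not test baseline malnutrition or sarcopenia. Under the assumed values, one FFMI(t) coefficient is significant in about 80% of trials when only level matters (rate ratio 0.67 per SD) and in about 10% when only decline matters. The direction follows from the algebra in step 3. The percentages rest on an event rate, a frailty variance and FFMI SDs that the protocol does not give.

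It would be too strong to call the 85 patients or the 80% invalid: both are right for the ΔFFMI correlation. This should be fixed before analysis, but it is a specification matter in an exploratory cohort.

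**What to change.** 1. In the Andersen-Gill model, enter baseline FFMI and within-patient change from baseline to the most recent visit as separate terms. In the joint model, report both the current-value and the slope association.
2. Keep the 12-month ΔFFMI for the same-year correlation with exacerbation rate and report it without temporal direction. It should not be a covariate for earlier hazard: that makes risk in month 1 depend on a month-12 measurement and drops patients without one.
3. Add a baseline term for malnutrition (NRS 2002) and/or sarcopenia (FFMI and HGS, cut-offs set in advance). Label it exploratory and give its detectable rate ratio. Show it with and without the planned stratification for nutritional support, which may absorb part of a malnutrition effect.
4. State in 4.1 that the 80% covers the ΔFFMI correlation only, and not the model coefficients.

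A small-sample variance correction, and an analysis of 0-6 month change against events in months 6-12, are optional.

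**Cost.** SAP wording only; the measurements are already scheduled. The visit-updated change term has less power than the correlation: about 66-69% at best, and less with uneven decline, measurement error or missed visits. At 15% prevalence the status term reaches 80% power only near a rate ratio of 3.0.

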4.2. Handling of missing data

The patients expected to be enrolled in the current study consist of patients from our previous THC cohort willing to participate in this extension study (approx. 100 patients). Assuming a dropout rate of 15% (including patients not willing to participate to the extension study as well as patients dropping out in the course of the study), we are expecting to enroll 85 patients in the study. Potential dropouts beyond 15% will not be replaced. If a patient withdraws her/his consent during the course of the study, no further data will be collected. However, data that have been collected before withdrawal will be used for the final analysis.

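### Section 4.2 labels 85 as the enrolment, but 85 is already net of on-study dropouts and fits section 4.1 only as the expected evaluable number

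*Combined protocol and SAP*

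**What the plan says.** Section 4.1 sets the target: "A sample size of 85 patients is envisaged to be able to detect a significant association". The association is a correlation of r = 0.30 between the patients' exacerbation rate and the change in "FFMI (1 year vs. baseline"), with 80% power at a two-sided 5% level. Section 3.3 gives the timing of the body-composition measurements: "These measurements will take place at baseline and after 6 and 12 months".

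Section 4.2 describes where the patients come from: "patients from our previous THC cohort willing to participate in this extension study (approx. 100 patients"). It then assumes a single 15% dropout rate, "including patients not willing to participate to the extension study as well as patients dropping out in the course of the study", and concludes: "we are expecting to enroll 85 patients in the study". Dropouts beyond 15% are not replaced. On withdrawal it says: "If a patient withdraws her/his consent during the course of the study, no further data will be collected". Data gathered up to that point remain in the final analysis.

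Sections 3.1 and 3.2 also admit newly recruited COPD patients, without giving a number. Section 4.2 does not count them.

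**The concern.** The 15% has two parts: patients who never join, and patients who join and later leave. Only the first part reduces enrolment. Taking both off and calling the remainder the number to enroll is coherent only if nobody leaves during the study, and section 4.2 itself says that some of the 15% do.

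The label matters because 85 is also the number on which the power rests. The powered quantity needs an FFMI value at 12 months. A patient who withdraws consent before then has no such value, because collection stops at withdrawal. If staff take 85 as the recruitment target and stop there, the power calculation has no allowance for missing 12-month measurements. The enrolment that would be needed appears nowhere in the plan, and neither does the split of the 15% into refusals and on-study loss.

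**Working it through.** **Inputs.** From section 4.1: r = 0.30, 80% power, two-sided 5%, target 85, variable = one-year change in FFMI. From section 4.2: approx. 100 THC patients, 15% total loss. The plan gives no on-study loss rate on its own, so the 5%, 10% and 15% used in steps 4 and 5 are assumptions.

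**Step 1. Reproduce the sample size (Fisher z).**
n = ((1.960 + 0.842) / atanh(0.30))² + 3, with atanh(0.30) = 0.3095. This gives n = 84.93, rounded up to 85. The plan's figure is reproduced.

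**Step 2. Reproduce the loss calculation.**
100 x (1 - 0.15) = 85, and in reverse 85 / 0.85 = 100. This is also correct. The number obtained is what remains after every loss in the 15%, including losses during the study.

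**Step 3. Power if 85 are evaluable.**
Power = Φ(atanh(0.30) x √(n - 3) - 1.960). At n = 85: 0.3095 x 9.055 - 1.960 = 0.843, so power is 80.0%. An exact calculation under bivariate normality gives 80.5%.

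**Step 4. Power if 85 is the enrolment and some are lost on study.** Evaluable numbers are rounded down.

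| Assumed on-study loss | Evaluable | Power (Fisher z) |
|---|---|---|
| none | 85 | 80.0% |
| 5% | 85 x 0.95 = 80.75, so 80 | 77.5% |
| 10% | 85 x 0.90 = 76.5, so 76 | 75.3% |
| 15% | 85 x 0.85 = 72.25, so 72 | 72.9% |

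For one or two losses, Fisher z gives 79.6% at 84 and 79.1% at 83; the exact method gives 80.0% and 79.6%. The exacerbation rate is count-based, so differences of tenths of a percent should not be over-read. The correlation detectable with 80% power, tanh(2.802 / √(n - 3)), is 0.309, 0.317 and 0.325 at 80, 76 and 72 evaluable.

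**Step 5. Enrolment that leaves 85 evaluable.**
Enrolment = 85 / (1 - on-study loss), rounded up:
- 5% loss: 89.5, so 90
- 10% loss: 94.4, so 95
- 15% loss: 100

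The figure equals 85 only when the on-study loss is zero. These targets apply whatever the source of the patients, THC cohort or new referrals.

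**The case against.** The best defence is that the sentence explains itself. It states that the 15% includes on-study dropouts, so a careful reader sees that 85 is a net figure, and on that reading the power is as stated. That stands, and it is why the point is small. It does not make *enroll* the right word, and it does not supply the missing enrolment target.

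Data collected before withdrawal are kept, and the Andersen-Gill, joint and mixed models can use partial follow-up. That also stands for those analyses. It does not supply the 12-month change for which 85 was calculated.

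Three stronger readings are tempting, and the documents do not support them:

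- **The study is underpowered.** A reader might infer this from the table above. The lower figures arise only if recruitment really stops at 85 and the assumed losses then occur. The study is also described as exploratory, and new recruits could offset losses.
- **Section 4.2 states two enrolments, approx. 100 and 85, and deducts unwilling patients from a group already defined as willing.** This depends on attaching the approx. 100 to the willing patients. It can equally describe the THC pool to be approached, and the deduction of refusals in the next sentence favours that. The phrasing is unclear, but a contradiction is not established.
- **Enrolment must lie between 85 and 100.** That would hold only if the approx. 100 THC patients were the sole source. Sections 3.1 and 3.2 allow new patients, so the plan sets no such bound.

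**Conclusion.** Wrong as written, but minor. Section 4.2 puts an enrolment label on a number that is already net of on-study dropouts. For the power in section 4.1, 85 has to be the expected number with FFMI at both baseline and 12 months. It can also be the enrolment only if there is no on-study loss, which is not what section 4.2 assumes.

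The sample-size arithmetic needs no correction, and the 80% power stands if 85 are evaluable. The exposure is confined to taking 85 literally as the point at which recruitment stops: a shortfall of roughly 2.5 to 7 percentage points of power for on-study losses of about 5% to 15%. Those rates are assumed here, not taken from the plan, and the power figures rest on the Fisher z approximation.

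**What to change.** In section 4.2:

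1. State that 85 is the expected number of patients with FFMI at baseline and 12 months, for the power calculation only. Add that this does not define a completers-only analysis set, since data from before withdrawal are still used.
2. Say what the approx. 100 represents. If it is the THC pool to be approached, say so; this also settles the wording about willing and unwilling patients.
3. Replace the 85 to be enrolled with an enrolment target equal to 85 plus the expected on-study loss. Give that loss separately from refusals, and count both THC patients and the new patients allowed in sections 3.1 and 3.2.

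If 85 enrolled is really meant, keep it and restate the power in section 4.1 for the evaluable number the sponsor expects.

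The first option is a wording change that leaves the calculation in section 4.1 untouched, although the sponsor has to commit to an on-study loss rate. The cost of the second is a slightly less favourable stated power.
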